Study Title: A PILOT STUDY TO EVALUATE THE EFFICACY OF VACUUM-ASSISTED DRESSINGS (V-AD) IN THE MANAGEMENT OF OPEN CHEST WOUNDS

Version date: 5/7/2018

NCT02803164

Protocol V1.7, 5/7/2018

A. GENERAL STUDY INFORMATION

A.1. Study Title: A PILOT STUDY TO EVALUATE THE EFFICACY OF VACUUM-ASSISTED DRESSINGS (V-AD) IN THE MANAGEMENT OF OPEN CHEST WOUNDS

A.2. Investigators

A.2.1. Principal Investigator: [name]

Coordinator: [name]

Statistician: [name], MS

A.2.2. Co-Principal Investigator: [name], MPH

Coordinator: [name]

B. STUDY PURPOSE

B.1. Hypothesis: Vacuum-assisted dressings (V-AD) are effective in treating patients with open chest wounds (OCW) and will decrease the time-to-closure of such wounds when compared to a historical cohort of patients managed by traditional wound care management.

B.2. Aims:

- Obtain definitive evidence for the effectiveness of V-AD in the management of OCW through a well-designed prospective pilot study conducted at 2 campuses of Mayo Clinic (Florida and Rochester).
- b. Compare the rate of healing (time-to closure) of OCW in patients treated with V-AD to a historical cohort of patients with OCW treated at Mayo Clinic without V-AD. Time to wound closure further being defined as the total approximation of the wound edges to close the defect.
- c. Determine if treatment with V-AD reduces the need for additional procedures to close wounds, such as muscle flaps.

C. BACKGROUND

Pleural space infections (empyemas) can occur either spontaneously or in the postoperative setting after any type of thoracic or abdominal surgery. The management of infected thoracic cavities has been one of the most frustrating problems encountered by thoracic surgeons. Post-operative infections occurring in the presence of concomitant bronchopleural fistulas (BPF) increase the complexity of treatment even more. While in many cases of empyema temporary drainage and antibiotic therapy will help resolve the infection, in others a more permanent drainage method such as an open chest window (a.k.a Eloesser window) may be required. The resulting open chest wounds

require frequent debridement and daily dressing changes for unspecified duration, imposing a tremendous financial and mental burden on the caretakers and patients. In addition, access into the chest cavity during dressing changes can be difficult and painful, which can result in small pockets of undrained infection.

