After obtaining informed consent from eligible patients, they will be taken to the operating room for the initial assessment and treatment as determined by the surgeon. The intervention may include, but is not limited to, thoracotomy, minimally invasive thoracic surgery, washout, excisional debridement, pulmonary decortication, pulmonary resection and closure of any obvious bronchopleural fistulas. Aerobic and anaerobic tissue cultures from the infected space will be obtained at the time of surgery. The surgeon will determine if the chest can be closed primarily. If unable to do so due to obvious infection or perceived high risk of developing a subsequent deep space abscess, the surgeon will next assess whether the wound is suitable for management with V-AD (V.A.C.* Therapy, KCI, San Antonio, TX). In the absence of any contraindications, the OCW will then be packed with one or more foam sponges and an airtight transparent dressing. At the time of application, these sponge dressings can be cut to fit within the wound. The type of dressing (black or white foam) to be used will be determined by the surgeon depending on the characteristics of the wound bed. The dressing will then be connected to the negative pressure canister unit and maintained on continuous negative pressure ranging from -75 mmHg to -125 mmHg. Unless otherwise indicated, the dressing will be changed once every 72 hours under IV sedation or anesthesia.

The patient will be admitted to the hospital for at least two supervised dressing changes, at which time the surgeon will re-assess the wound to determine if it can be closed with or without a soft tissue (muscle, omentum, etc.) flap. Wounds determined to be not ready for closure will then be repacked with the V-AD. If no other indication for inpatient hospital care exists other than the V-AD, the patient will be then discharged home or to a skilled nursing facility where the remainder of dressing changes will be performed. If the patient cannot be safely discharged from the hospital, inpatient care will be continued.

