After discharge, the patient will return to the outpatient clinic for wound inspection and dressing change by the surgeon once every two weeks and earlier, if necessary. During hospitalization and clinic visits, a Mayo Clinic photographer or a provider authorized to use the Mayo Clinic imaging software will photograph the wound, which will be a part of the permanent medical record of the patient. At every dressing change in and outside the hospital, the number of individual pieces of foam sponges will be entered in a logbook and accounted for during removal at the next change.

Figure 1: Algorithm for Patient Selection and Enrollment

E.1.2.2. Monitoring:

A prospective database of all patients in the study will be maintained and will record the following:

- a. Name, Medical Record number and Dates of dressing changes
- b. Pain scores visual analogue scores,
- c. Ease of dressing changes (Easy, moderately difficult, very difficult)
- d. Wound bed characteristics including amount of granulation tissue (minimal, moderate and significant) and dimensions (length x breadth x depth in centimeters).
- e. Duration of treatment
- f. Adverse events

E.1.2.3. Discontinuation of V-AD therapy:

1. In the absence of a noticeable improvement in the wound bed after 2 weeks of continuous V-AD therapy, the treatment plan will be re-assessed and the determination will be made as to whether the V-AD therapy should be discontinued.

2. The V-AD will be discontinued if the patient develops severe uncontrolled pain that does not respond to pain medications or a reduction in the negative pressure to -50 mm Hg.

3. In the event of any unpredicted adverse event, such as bleeding, injury to underlying organs, new onset of respiratory distress or allergy to the dressings will result in removing the V-AD.

4. Patients who require treatment with anticoagulation or antiplatelet agents after V-AD application will be removed from the study to avoid hemorrhagic complications.

F. DRUGS/ SUBSTANCES/ DEVICES

The V.A.C. Therapy System has many components that work together to apply negative pressure to wounds. The components include:

- 1. a porous foam dressing which comes in contact with the wound base and equally distributes negative pressure throughout the wound,
- 2. an airtight transparent adhesive drape that covers the foam dressing and
- 3. a software-controlled V.A.C Canister that is connected to the dressing by means of a transparent plastic tubing.

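### Surgeon wound assessment is scheduled for V-AD patients only and no common rule dates closure, so closure by secondary intention may be dated with different delays in the two groups

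*Combined protocol and SAP*

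**What the plan says.** Aim b in B.2 is to "Compare the rate of healing (time-to closure) of OCW in patients treated with V-AD to a historical cohort of patients with OCW" managed without V-AD. The same item defines the endpoint: "Time to wound closure further being defined as the total approximation of the wound edges to close the defect". That describes a state of the wound. It does not say from when time is counted, who judges closure, or which date is used when nobody saw the wound close.

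For V-AD patients, E.1.2.1 gives a schedule:

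- In hospital: "The patient will be admitted to the hospital for at least two supervised dressing changes, at which time the surgeon will re-assess the wound" and "determine if it can be closed with or without a soft tissue (muscle, omentum, etc.) flap".
- Dressing interval: "Unless otherwise indicated, the dressing will be changed once every 72 hours under IV sedation or anesthesia".
- Outpatient: "After discharge, the patient will return to the outpatient clinic for wound inspection and dressing change by the surgeon once every two weeks", or sooner if needed.

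The E.1.2.2 database records dates of dressing changes, wound dimensions and duration of treatment. It lists neither a closure date nor the date a wound was last seen open.

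For controls, D.1 and G say only that 10 past patients will be selected by matching. They do not say how often those wounds were assessed, by whom, or how a closure date will be taken from the chart. The only remark on frequency under traditional care is in the Background (section C), which mentions daily dressing changes. Section G is descriptive and says nothing about dating closure.

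**The concern.** If a wound closes between two assessments and is dated at the second, its recorded time is too long by part of the gap. With the same gaps in both groups the delay largely cancels. Here one group has a protocol schedule and the other has whatever was charted, so any difference in spacing enters the comparison as if it were a treatment effect. Propensity matching balances who the patients were, not when their outcome was looked for.

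Time to closure is the outcome named in the hypothesis, H.2 calls efficacy the primary endpoint, and G carries forward whatever shows promise. With 10 patients per group compared by eye, nothing in the plan would show a reader that part of a difference came from assessment spacing.

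**Working it through.** The plan states no effect size, power or closure-time distribution, so there is no figure of its own to reproduce. The check asks how large the distortion could be when treatment has no effect.

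**Inputs from the documents:** V-AD assessment by the surgeon every 14 days after discharge; V-AD dressing changes at 72 hours (about days 3 and 6 for the first two); 10 patients per group; closure by secondary intention taking months or even years (section C).

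**Assumed inputs:** control spacing from daily to about 13 weeks; true median closure 12, 26 or 52 weeks; distribution as stated in each step.

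**Step 1, mean delay.** If closure is dated at the next assessment, the mean delay is about half the interval. With control interval Ic in days, the spurious difference (control minus V-AD) is (Ic − 14)/2:

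- daily: (1 − 14)/2 = −6.5 days
- weekly: (7 − 14)/2 = −3.5
- 14 days: 0
- 28 days: +7
- 56 days: +21
- 91 days: +38.5

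The sign changes at 14 days.

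**Step 2, relative size.** True closure times are lognormal with log SD 0.8, identical in both groups. Each is rounded up to the next assessment: every 2 weeks for V-AD, every Ic for controls. Apparent shortening = 1 − (geometric mean V-AD / geometric mean control). Negative means V-AD looks slower.

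| Control assessment | Median 12 wk | Median 26 wk | Median 52 wk |
|---|---|---|---|
| Daily | −10% | −5% | −2% |
| Weekly | −5% | −2% | −1% |
| Every 2 weeks | 0 | 0 | 0 |
| Every 4 weeks | 8% | 4% | 2% |
| Every 8 weeks | 20% | 12% | 7% |
| Every 12 weeks | 31% | 18% | 10% |

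**Step 3, surgical closures.** An operation has an exact date, so it carries no dating delay. If half of closures in each group are surgical, the log ratio halves and the ratio becomes its square root. At a 12-week median, 8-week control assessment gives 1 − √0.80 = 11%, and 12-week gives 1 − √0.69 = 17%.

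**Step 4, 10 v 10 with another distribution.** Weibull times (shape 1.5), V-AD assessed at days 3 and 6 and then every 14 days, controls assessed at a random phase (daily dating uses the next whole day). The probability that the V-AD median looks faster with no true effect (0.50 means no bias) is:

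| Control assessment | Median 90 days | Median 365 days |
|---|---|---|
| Daily | 0.43 | 0.48 |
| 14 days | 0.50 | 0.50 |
| 28 days | 0.57 | 0.52 |
| 56 days | 0.73 | 0.56 |
| 91 days | 0.86 | 0.61 |

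The 14-day row also shows the effect of a common grid: the spurious difference returns to about zero.

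**The case against.** The strongest reply is that nothing shows controls were assessed less often. That is correct. A reader might infer that controls were seen only at sparse routine visits, so that V-AD will look faster with no effect. The documents do not support this: they give no control schedule, and their one remark on frequency is daily dressing changes. That remark does not say that a surgeon looked or that closure was charted, but it keeps open a bias against V-AD.

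Four further objections have force:

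- **Surgical closure.** The Background says procedures to speed closure are often performed, and the surgeon may close a V-AD wound at re-assessment. Late dating therefore applies to secondary-intention closures only.
- **V-AD timing.** The schedule allows for other indications and for earlier visits. Dressings are also changed about every 72 hours, so closure might be noted between surgeon visits. The two-week grid is a working assumption.
- **Exact dates.** A reader might infer that the plan treats recorded closure dates as exact. It does not say so; G is silent.
- **Noise.** With log SD 0.8 and 10 per group, the standard error of the log ratio is 0.8 × √(2/10) = 0.36, so a 95% interval spans a factor of exp(1.96 × 0.36) ≈ 2 either way. Chance error exceeds the biases shown.

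These limit the size and remove any claim about direction. They do not remove the point. Imprecision does not excuse an avoidable systematic difference, and a descriptive pilot meant to guide follow-up studies should be able to show whether one is present.

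**Conclusion.** The concern holds in conditional form. The plan sets surgeon assessment for one group only and gives no common dating rule, so the time-to-closure comparison is open to bias unless assessment spacing happens to match. It favours V-AD if control wounds were assessed less often than every two weeks, and runs slightly against V-AD if closure was charted at daily dressing changes.

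Over the assumed ranges, with all closures by secondary intention, the apparent effect runs from V-AD 10% slower to 31% faster at a 12-week median, and from 2% slower to 10% faster at 52 weeks. Against closure times of many months it is small unless control assessments were some 8 to 13 weeks apart. Control spacing, the closure-time distribution, the medians and the share of surgical closures are all assumptions. This is an inexpensive improvement worth making, not a finding that the result will be wrong.

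**What to change.** **E.1.2.2 and the control chart form.** For every patient record the date the wound was last documented open, the date it was first documented closed, and whether closure was surgical. For a surgical closure both dates equal the operation date.

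**Section G.** State that:

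- closure time in both groups is summarised as lying between these two dates (interval-censored);
- as a sensitivity check, secondary-intention closure dates in both groups are rounded up to one common prespecified grid, for example the median control assessment interval;
- the number and spacing of documented wound assessments and the proportion of surgical closures are tabulated by group.

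**Cost.** Wound-assessment dates must be abstracted from 10 control charts, and the interval around the group difference becomes slightly wider. No change to patient care is involved.

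**What it does not cure.** Because the surgeon decides on closure at these assessments, more frequent assessment may also bring surgical closure forward. Better dating cannot separate that from the effect of the dressing, and it should be stated as a limitation.

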A total of 10 patients will be enrolled in the intervention (V-AD) arm of the study. These patients will be recruited from those presenting to Mayo Clinic Florida or Mayo Clinic Rochester with thoracic infections that require surgical intervention. A historic control group of 10 patients with open chest wounds who were treated with the traditional treatment techniques at Mayo Clinic will be selected using propensity-matching methods. We plan to complete our target accrual over a timeframe of approximately 12 months.

D.2. Subject Population

Subjects will be identified by the Principal Investigator or the Co-Investigators. Patients referred for surgical management of thoracic infections, who meet inclusion criteria and none of the exclusion criteria, will be invited to participate in the study. If the subject is interested in more information about

the study, a study coordinator will meet with the patient to discuss further and obtain informed consent.

D.3. Inclusion criteria

- 1. Subject provides informed consent and is:
 - a. >18 years of age,
- 2. Subject is scheduled to undergo surgical intervention(s) as part of the standard care for management of intrathoracic infection.

D.4. Exclusion criteria:

- D.4.1. Patients who have the following conditions will be excluded from participating:
 - 1. Patent bronchopleural fistulas.
 - 2. Severe respiratory failure requiring mechanical ventilation at the time of first consultation.
 - 3. Inability to provide informed consent due to physical or mental impairment.
 - 4. Altered mental status.
 - 5. Proven or suspected malignancy in the wound.
 - 6. Coagulopathy due to medical or pharmacologic reasons.
 - 7. Dependency on anticoagulants or antiplatelet medication due to high risk for adverse events if these medications are stopped for a prolonged period of time.
 - 8. Allergy to acrylic products.
 - 9. Subject is a pregnanat or lactating female

D.4.2. Patients in whom the use of V-AD is determined to be unsafe by the surgeon for any reason will be excluded from the study.

D.5. INITIAL EVALUATION AND INFORMED CONSENT FOR ENROLLMENT

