There are 2 types of foam dressings that will be used in the study:

- 1. An open pore reticulated polyurethane foam (V.A.C Granufoam Dressing)
- 2. A polyvinyl alcohol foam (V.A.C WhiteFoam Dressing).

The canister system is self-monitoring and can be set to different therapy modes (continuous or intermittent) depending on the individual patient and wound needs. In-built alarm systems can detect a loss of pressure or tubing blockage, alerting the care team to troubleshoot these issues.

G. DATA ANALYSIS

Exploratory analysis will be used to analyze the correlative studies comparing the healing rates. The analysis will include all 10 patients treated with V-AD and a matched group of 10 patients previously treated for empyema at Mayo Clinic. Due to the limited sample size the analysis will be descriptive and hypothesis generating. Any information that shows promise based on the pilot data will be explored in follow-up studies. Descriptive statistics, and scatter plots with 95% confidence intervals will graphed over time. Data will be visually inspected for differences.

The following datasets will be compared during analysis:

1. V-AD treated patients versus historical controls.

H. RISKS

H.1. Potential risks: The specific risks of V-AD use in the chest cavity have been reported and include pain, hypotension and difficulty in removing the sponge (11). No serious adverse events have been reported to date. General risks of NPWT when applied to other parts of the body include suction injury to skin and injury to underlying organs such as bowel or blood vessels. Extrapolating these adverse effects to the chest, there is an unquantifiable risk of injury to intrathoracic organs – lungs, heart, large vessels (aorta, pulmonary artery or veins). Hypothetically, injury to the lungs can lead to worsening of bronchopleural fistulas, air leaks or pulmonary hemorrhage; injury to the vascular structures can lead to significant hemorrhage, and even death. During removal of the black foam sponge dressing, it is possible to cause injury to the underlying structures due to excessive traction or adherence from tissue ingrowth.

H 1.1. Potential Severe Adverse Events

- Death
- Respiratory failure requiring ventilation (for any cause)
- Major cardiac arrhythmias requiring cardioversion or hospitalization which are hemodynamically significant.
- Massive Hemoptysis (life-threatening or requiring an intervention e.g. embolization)

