- Intra-parenchymal/intrapleural hemorrhage leading to hemodynamic instability or requiring any intervention to specifically address the bleeding.
- All new onset bronchopleural fistulas will be reported as SAE's.
- Worsening of pleural space infection requiring treatment with IV antibiotics, with exceptions as below:
 - Treatment of pathogens identified on microbiology obtained during the initial culture will not count as a new infection.
 - Requirement for sharp debridement of necrotic tissue or exudates identified during dressing changes will not be considered an adverse event, as this is normal during management of infected wounds.

H.1.2. Other Adverse Events

- Minor cardiac arrhythmias NOT requiring cardioversion, hospitalization and/or are NOT hemodynamically significant.
- Minor Hemoptysis or minor intra-parenchymal/intrapleural hemorrhage
- Pneumonia/pleural space infection treated as outpatient
- Mild (<4/10, not requiring IV medication) to moderate pain (requiring IV medication or rated as >5/10)
- DVT or Pulmonary Embolus treated with anticoagulation alone

H.2. Risk Prevention and Monitoring: In order to decrease the risks of these potential adverse events, the following safety precautions will be taken:

- 1. The dressings will not be applied directly in contact over any exposed blood vessels, heart or lung, or anastomotic sites.
- 2. Mepitel[®] (Mölnlycke Health Care, Norcross, GA), a silicone-based perforated non-adherent dressing will be placed over any delicate organs such as the heart or the lung. This will prevent adherence of the foam dressing to the underlying tissue while allowing drainage. Mepitel[®] itself can be easily removed as it is non-adherent.
- 3. The black foam dressing will not be used directly over any organ/structure likely to be traumatized during removal of the dressing. Instead, the white foam will be used as the first layer. The black foam may be placed over the white foam in such instances.
- 4. Prior to removal, the dressings will be thoroughly soaked with normal (0.9%) saline to disengage the dressings easily.

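### Item 4 of E.1.2.3 takes a treated V-AD patient out of the study while section G analyses all 10 treated, and the plan does not say whether such a patient is still followed and analysed

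*Combined protocol and SAP*

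**What the plan says.** Section E.1.2.3 lists four situations in which V-AD may end.

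- Item 1 applies "In the absence of a noticeable improvement in the wound bed after 2 weeks of continuous V-AD therapy" and leads to a reassessment of the treatment plan.
- Items 2 and 3 end V-AD for uncontrolled pain or for an unpredicted adverse event.
- Item 4 differs in its object: "Patients who require treatment with anticoagulation or antiplatelet agents after V-AD application will be removed from the study to avoid hemorrhagic complications".

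Section G defines the analysis group by treatment received: "The analysis will include all 10 patients treated with V-AD", next to 10 matched historical controls. It adds: "Due to the limited sample size the analysis will be descriptive and hypothesis generating".

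On follow-up, section E.1.2.1 says that after discharge "the patient will return to the outpatient clinic for wound inspection and dressing change by the surgeon once every two weeks", or earlier if needed. Section H.2 collects adverse events until one week after either closure or the end of V-AD. No section says whether closure is still ascertained once V-AD has ended with the wound open.

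**The concern.** Time to closure is the subject of the hypothesis and of aim b, and aim c concerns flaps and other closure procedures. Aim b defines closure by approximation of the wound edges, so the outcome exists whether or not V-AD is still in place. A rule that takes a treated patient out of the study is therefore a post-treatment exclusion, unless the plan says that the patient's outcomes are kept.

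With 10 patients and no stated dropout allowance or replacement rule, losing one removes a tenth of the arm. The two campuses could also apply item 4 differently, one taking off the device and the other closing the patient's record, and neither would depart from the text.

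**Working it through.** **Stated figure.** The V-AD arm has 10 patients (D.1, E.1, G). No alpha, power or effect size stands behind this number, so there is no calculation to reproduce. The check is a comparison of the texts, with illustrations of size.

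**Two readings of item 4, with k patients meeting it.**

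| Reading | Patients analysed | Agrees with section G? |
|---|---|---|
| Patient leaves the study, outcomes not kept | 10 − k (9, 8 or 7 for k = 1, 2, 3) | No |
| Device ends, patient and data stay | 10 | Yes |

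Each patient counts for 1/10 = 10% of the arm.

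**Can item 4 occur?** Exclusion 6 in D.4.1 covers coagulopathy. Exclusion 7 covers "Dependency on anticoagulants or antiplatelet medication due to high risk for adverse events if these medications are stopped" for long. Both act at entry. Section H.1.2 then lists "DVT or Pulmonary Embolus treated with anticoagulation alone" among adverse events that may arise later, and that treatment meets item 4. The documents give no rate. At an assumed per-patient chance p, the probability of at least one case in 10 is 1 − (1 − p)^10:

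- p = 5%: 40%
- p = 10%: 65%
- p = 20%: 89%
- p = 30%: 97%

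**Direction, without a distribution.** Assume that 7 of 10 wounds close by some cut-off, or 70% (exact 95% interval 35% to 93%). The plan defines no such proportion, so this is illustration only.

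- Dropping 1, 2 or 3 patients with open wounds gives 7/9 = 78%, 7/8 = 88%, 7/7 = 100%.
- Dropping 1, 2 or 3 patients whose wounds would have closed gives 6/9 = 67%, 5/8 = 63%, 4/7 = 57%.

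**Direction, for time to closure.** Assume exponential times with mean 1. The expected ordered times are E[X(j)] = sum over i = 0 to j − 1 of 1/(10 − i): 0.100, 0.211, 0.336, 0.479, 0.646, 0.846, 1.096, 1.429, 1.929, 2.929. They sum to 10, so the mean is 1.000. The median is (0.646 + 0.846)/2 = 0.746. With k = 1, 2, 3 lost:

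- Loss unrelated to healing: mean ratio 1.000 throughout; median ratio 1.000, 1.019, 1.019. This is about no bias.
- Loss at random from the slower half (average 1.646): mean (10 − 1.646k)/(10 − k) = 0.928, 0.839, 0.723; median ratio 0.866, 0.754, 0.642.
- Loss at random from the faster half (average 0.354): mean (10 − 0.354k)/(10 − k) = 1.072, 1.161, 1.277; median ratio 1.134, 1.302, 1.469.

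For scale, the sampling SD at n = 10 is 1/√10 = 32% for the mean and 42% (simulated) for the median. The slower-half shifts all lie below one SD. The sign of the shift follows entirely from which half is assumed lost, and nothing in the documents links the need for these agents to healing speed.

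**Would closure still be captured after V-AD ends?** The two-weekly visits in E.1.2.1 include wound inspection and are not limited to patients on V-AD. Photographs from clinic visits go into the permanent record. However, no end of the visits is stated, and nothing says that they continue for a patient whose V-AD has ended or who has been taken out of the study. The E.1.2.2 database holds treatment duration and wound dimensions but neither closure date nor closure method. Treatment duration may approximate time to closure when V-AD runs until closure, but not when V-AD ends first.

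**The case against.** The harmless reading of item 4 has good support. The item stands under a heading about ending V-AD therapy. Its stated purpose, avoiding bleeding, is served by taking the device off and not by discarding data. Section G defines its group by treatment received. The adverse-event window runs past the end of V-AD, which sits badly with immediate exit from the study. All of this stands, and it rules out calling the texts a strict contradiction. It does not settle the meaning: items 1 to 3 speak of the therapy or the device, item 4 speaks of the patient and the study, and the adverse-event window does not cover closure.

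It is also fair that the analysis is descriptive, with no test or decision rule, and that visits, photographs and the chart may well hold the closure outcome. The first point limits the harm to description. The second means that loss of outcomes is possible but not demonstrated.

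A reader might go further and infer that the plan drops patients who respond poorly under item 1, and so flatters V-AD. The documents do not support that. Item 1 removes nobody from the study. V-AD would have to be stopped, closure would have to go unascertained, and the patient would have to be dropped despite section G. The last two steps are stated nowhere. The slower-half figures therefore show only what such a loss could do.

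**Conclusion.** The point holds as an unresolved ambiguity that should be corrected. Followed as written, item 4 excludes a treated patient, departs from section G and loses closure and safety outcomes. Followed as device removal, it does none of these, and the plan does not choose between the two.

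The firm part of the size is that each affected patient is 10% of the arm. The number affected is unknown, since the documents give no rate. The direction of any bias from item 4 is also unknown, and if the trigger is unrelated to healing there is about none. The percentages shown rest on assumed loss counts, an assumed closure proportion and exponential closure times, and the conclusion does not depend on them. Type I error and power are not at issue. The defect is not fatal to a pilot, but closure outcomes that are not collected may not be recoverable later.

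**What to change.** Reconcile item 4 with section G by separating the end of V-AD from leaving the study. This takes no view on when V-AD should stop or on anticoagulant use. Possible text:

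> Every patient who received V-AD, including those whose V-AD ends early under items 1 to 4, is followed for closure date and closure method through the existing clinic visits, telephone contact or chart review until closure, death or [cut-off set by the sponsor], unless consent is withdrawn. All are analysed in the V-AD group.

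**Cost.** A few sentences, and modest extra follow-up for the few patients whose V-AD ends early, bounded by the cut-off. The closure result may look less favourable than if such patients were left out.

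**Secondary clarifications, separate from the main point.**

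- Add closure date and closure method to the E.1.2.2 database. Aims b and c need both, and at dressing changes E.1.2.1 already has the surgeon assess the wound to "determine if it can be closed with or without a soft tissue (muscle, omentum, etc.) flap".
- State which end of the H.2 adverse-event window applies when V-AD ends before closure. The sponsor chooses. If closure is chosen, monitoring could last for months given the healing times in section C, and under H.3.1 each severe event in that time would put the study on hold.
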